4. INVESTIGATIONAL PRODUCT(S)

The term ‘study treatment’ is used throughout the protocol to describe GSK2857916 as the investigational product (IP) received by the subject as per the protocol design.

4.1. Description of Investigational Product

Product name :	GSK2857916 Solution, 20 mg/mL, 1.5mL anti-BCMA-ADC
Formulation description:	Solution containing 20mg/mL GSK2857916
Dosage form :	Supplied as frozen liquid. Recommended storage condition is -50°C to -15°C.
Unit dose strength(s)/Dose Level(s):	20mg/mL, 1.5mL (Refer to Section 3.3.1.2.1 for dose levels)
Physical Description:	GSK2857916 Solution for Infusion is clear or opalescent; colorless, yellow to brown liquid
Route/ Administration/ Duration:	Delivered as IV solution (see Section 3.8)
Dosing instructions:	Dilute GSK2857916 solution in normal 0.9% saline to the appropriate concentration for the dose. See Section 4.2 for compatible administration materials. Doses of GSK2857916 are to be administered as an IV infusion via an infusion pump that can ensure precision to the decimal point of a mL for the infusion rate at lower doses. It is recommended to prime the tubing with at least 15 mL prior to dosing.
Manufacturer/ Source of Procurement:	GSK
Batch Lot number	132373860

GSK2857916 will be provided to sites by GSK. **Only Batch Lot# 132373860 of drug product will be used for this trial.** The contents of the label will be in accordance with all applicable regulatory requirements. **The lot number indicated on the label refers to labelled lot number; the batch Lot# 132373860 may not be provided on the label.**

4.2. Preparation/Handling/Storage of GSK2857916 Investigational Product

Preparation

GSK2857916 Solution for Infusion, 20 mg/mL is supplied as a frozen liquid (Lot# 132373860). Before use, thaw each vial of GSK2857916 for Infusion, 20mg/mL, 1.5mL for up to 4 hours under refrigerated conditions (2-8°C), protected from light. Following thawing, gently swirl the vial to ensure uniformity. GSK2857916 should be diluted in normal saline (0.9%) to no more than 2 mg/mL and no less than 0.2 mg/mL. Refer to the Study Procedures Manual (SPM) for further details on preparation of GSK2857916.

The dosing solution of GSK2857916 can be held under refrigerated conditions (2-8°C), for up to 24 hours (**NOTE:** For centers in Canada up to 8 hours only) or 4 hours at

ambient temperature (diluted drug product in bag) from a stability perspective, but should be used as soon as possible as the product does not contain an antimicrobial preservative.

Handling

Under normal conditions of handling and administration, investigational product (IP) is not expected to pose significant safety risks to site staff. A Material Safety Data Sheet (MSDS) describing the occupational hazards and recommended handling precautions will be provided to site staff if required by local laws or will otherwise be available from GSK upon request.

In the case of unintentional occupational exposure notify the study monitor, the GSK Medical Monitor and/or the study manager.

Refer to the SPM for detailed procedures for the disposal and/or return of unused study treatment(s).

Administration

GSK2857916 is compatible with polyvinylchloride-lined or polyolefin-lined intravenous infusion administration sets, 0.2 micron polyethersulfone filters, or optionally a polyurethane catheter. Doses of GSK2857916 are to be administered as an IV infusion via an infusion pump that can ensure precision to the decimal point of a mL for the infusion rate at lower doses. It is recommended to prime the IV tubing with at least 15 mL prior to dosing.

Administration of drug product in this trial is restricted to Manufacturer Batch Lot#132373869.

Storage

GSK2857916 must be stored in a secure area under the appropriate physical conditions for the product. Access to and administration of the GSK2857916 will be limited to the investigator and authorized site staff. GSK2857916 must be dispensed or administered only to subjects enrolled in the study and in accordance with the protocol.

GSK2857916 is to be stored at a temperature range of -50°C to -15°C. Maintenance of a temperature log is required.

The expiry date, where required, is stated on the product label.

4.3. Product Accountability

In accordance with local regulatory requirements, the investigator, designated site staff, or head of the medical institution (where applicable) must document the amount of investigational product (IP) dispensed and/or administered to study subjects, the amount returned by study subjects, and the amount received from and returned to GSK, when

applicable. Product accountability records must be maintained throughout the course of the study. Refer to the SPM for further detailed instructions on product accountability.

4.4. Treatment Compliance

GSK2857916 will be intravenously administered to subjects at the study site. The dose to be administered is based on body weight calculation, and may be reduced for toxicity according to protocol guidelines. Only two dose reductions are allowed per subject; the first dose reduction by 25%, and the second by an additional 25%. If subject is not tolerating treatment at 50% of scheduled dose the subject will be withdrawn from study. Additional dose reductions (beyond 50% of the original scheduled dose) may be possible only for subjects who have been enrolled during dose escalation in Part 1 at the highest dose, which was subsequently deemed as exceeding the MTD.

The actual body weight in kg will be used for dose calculation in all subjects whose body weight is ≤ 100 kg. For subjects with body weight > 100 kg, the dose to be administered should be the same as that calculated for a subject weighing 100kg. Administration will be documented in the source documents and reported in the electronic case report form (eCRF). The time of start and end of infusion will be documented in eCRF.

4.5. Treatment of Investigational Product Overdose

In the event of an overdose (defined as administration of more than the protocol-specified dose) of GSK2857916, the investigator should:

- contact the GSK Medical Monitor immediately
- closely monitor the subject for adverse events (AEs)/serious adverse events (SAEs) and laboratory abnormalities until GSK2857916 can no longer be detected systemically (at least 3 months for GSK2857916)
- obtain a plasma sample for pharmacokinetic (PK) analysis within 24 hours of the event if requested by the GSK Medical Monitor (determined on a case-by-case basis)
- document the quantity of the excess dose as well as the duration of the overdosing in the eCRF

Decisions regarding dose interruptions or modifications will be made by the investigator in consultation with the GSK Medical Monitor based on the clinical evaluation of the subject

5. STUDY POPULATION

5.1. Number of Subjects

The number of dose levels and the level at which the maximum tolerated dose (MTD) is reached cannot be determined in advance. An adequate number of subjects will be enrolled into the study to establish the recommended dose(s) for further study. It is estimated that approximately 30 subjects will be enrolled into Part 1, Schedule 1 (dose-

escalation) of the study. Up to 40 subjects with MM and up to 10 subjects with BCMA positive lymphomas (~50 subjects total) will be enrolled in Part 2 (expansion cohort). The number of subjects in the expansion cohort has been estimated based on expected variable expression of BCMA in those subjects (about 1/3 low, 1/3 medium, 1/3 high expression; approximately 13 subjects/group). The level of BCMA expression in a given subject is expected to impact target-mediated clearance, which as a consequence might be reflected in the PK/PD variability and safety profile of individual subjects. In addition, the sample size of 40 subjects in the MM cohort will allow for assessment of early signals of clinical activity and relationships (if any) to variable target expression levels. A total of approximately 80 subjects will be enrolled in the study. If Part 1, Schedule 2 (once weekly schedule) is explored, up to 15 additional subjects will be enrolled; then a total of approximately 95 subjects will be enrolled in the study.

In Part 1 (dose-escalation) of the study, if a subject has been withdrawn prior to expiration of the DLT observation period OR received less than 2/3 of the scheduled dose and is not evaluable for DLT, additional subjects may be enrolled as replacement subjects and assigned to the same treatment sequence at the discretion of the Sponsor in consultation with the investigator.

5.2. Subject Selection Criteria

5.2.1. Inclusion Criteria

Specific information regarding warnings, precautions, contraindications, adverse events (AEs), and other pertinent information on the GSK study treatment that may impact subject eligibility is provided in the Investigator Brochure (IB)/IB supplement(s). Deviations from inclusion criteria are not allowed because they can potentially jeopardize the scientific integrity of the study, regulatory acceptability or subject safety. Therefore, adherence to the criteria as specified in the protocol is essential.

Subjects eligible for enrolment in the study must meet all of the following criteria:

1. Provide signed written informed consent, which includes compliance with the requirements and restrictions listed in the consent form
2. Male or female, 18 years or older (at the time consent is obtained)
3. Eastern Cooperative Oncology Group (ECOG) performance status of 0 or 1 ([Appendix 6](#))
4. **Part 1/dose escalation:**
 - Histologically or cytologically confirmed diagnosis of: Multiple Myeloma in a subject who fulfills **all** of the following:
 - has undergone stem cell transplant, or is considered transplant ineligible,
 - has been pretreated with at least the 3 following classes of anti-myeloma drugs: alkylators, proteasome inhibitors and immunomodulators,

- has demonstrated progression on, or within 60 days of completion of the last therapy.

Part 2 /MM cohort:

- Histologically or cytologically confirmed diagnosis of: Multiple Myeloma in a subject who fulfills **all** of the following:
- has undergone stem cell transplant, or is considered transplant ineligible,
- has been pretreated with at least the 3 following classes of anti-myeloma drugs: alkylators, proteasome inhibitors and immunomodulators,
- and has demonstrated progression on, or within 60 days of completion of the last therapy.
- AND has measurable disease with at least one of the following:
 - a. Serum M-protein ≥ 0.5 g/dL (≥ 5 g/L)
 - b. Urine M-protein ≥ 200 mg/24h
 - c. Serum FLC assay: Involved FLC level ≥ 5 mg/dL (≥ 50 mg/L) and an abnormal serum free light chain ratio (< 0.26 or > 1.65)
 - d. Biopsy proven plasmacytoma (should be measured within 28 days of Screening Visit)

or

Part 2/ BCMA positive Lymphoma cohort:

- a. Subject with one of the following hematologic malignancies: Diffuse Large B-cell Lymphoma DLBCL or Follicular Lymphoma that exhibits positive BCMA expression on tumor cells as determined by a central laboratory using a validated IHC assay. Eligible subjects with BCMA positive lymphomas must also fulfill the prior treatment requirements as follows:
 - b. DLBCL : at least 2 prior lines of systemic therapy containing at least one line of chemo-immunotherapy with anti-CD20 antibody, and either has undergone stem cell transplant or is considered transplant ineligible
 - c. FL: at least 2 prior lines of systemic therapies.
5. Subjects with a history of autologous stem cell transplant are eligible for study participation provided the following eligibility criteria are met:
 - a. transplant was > 100 days prior to study enrolment
 - b. no active infection
 - c. subject meets the remainder of the eligibility criteria outlined in this protocol
 6. Adequate organ system functions as defined in [Table 14](#).

Table 14 Adequate Organ System Function

System	Laboratory Values
Hematologic	
Absolute neutrophil count (ANC) ¹	≥ 1.0 X 10 ⁹ /L
Hemoglobin	≥ 8.0 g/dL
Platelets	≥ 50 X 10 ⁹ /L
Coagulation	
INR	≤1.5
PTT	≤1.5 x ULN
Hepatic	
Total bilirubin	≤1.5 X ULN (isolated bilirubin >1.5xULN is acceptable if bilirubin is fractionated and direct bilirubin <35%)
AST and ALT	≤ 1.5 X ULN
Renal	
Serum creatinine or Calculated creatinine clearance ²	<1.2XULN ≥ 60 mL/min for Part 1; ≥50 mL/min for Part 2 if data supports loosening criteria
Albuminuria	≤500mg/24hr
Cardiac	
LVEF (Echo)	≥50%
Troponin	≤1xULN

1. Without Growth factor support for the past 14 days, excluding erythropoietin

2. As calculated by Modified Diet in Renal Disease (MDRD) formula ([Appendix 5](#))

NOTE: Laboratory results obtained during Screening should be used to determine eligibility criteria. In situations where laboratory results are outside the permitted range, the investigator may opt to retest the subject and the subsequent within range screening result may be used to confirm eligibility.

7. A female subject is eligible to participate if she is of:
- Non-childbearing potential (i.e. physiologically incapable of becoming pregnant) defined as pre-menopausal females with a documented tubal ligation or hysterectomy; or postmenopausal defined as 12 months of spontaneous amenorrhea [in questionable cases a blood sample with simultaneous follicle stimulating hormone (FSH) > 40 MIU/mL and estradiol < 40 pg/mL (<147 pmol/L) is confirmatory]. Females on hormone replacement therapy (HRT) and whose menopausal status is in doubt will be required to use one of the contraception methods specified if they wish to continue their HRT during the study. Otherwise, they must discontinue HRT to allow confirmation of post-menopausal status prior to study enrollment. For most forms of HRT, at least 2-4 weeks will elapse between the cessation of therapy and the blood draw; this interval depends on the type and dosage of HRT. Following confirmation of their

- post-menopausal status, they can resume use of HRT during the study without use of a contraceptive method.
- Women of childbearing potential must have a negative serum pregnancy test within 72 hours of first dose of study treatment and agree to use effective contraception, as defined in Section 11.1.1, during the study and for 60 days following the last dose of study treatment.
8. Men with a female partner of childbearing potential must have either had a prior vasectomy or agree to use effective contraception as described in Section 11.1.2 from the time of first dose of study until 60 days after the last dose of study treatment to allow for clearance of any altered sperm.
 9. All prior treatment-related toxicities (defined by National Cancer Institute-Common Toxicity Criteria for Adverse Events (NCI-CTCAE), version 4) must be \leq Grade 1 at the time of enrollment except for alopecia, and grade 2 neuropathy

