7.1.2. Dose Expansion

7.1.2.1. Every 3 Weeks Dosing Schedule for Multiple Myeloma

	Time and Events Table for Full Study (Cycle = 21 days)								
Study Assessments ¹	Screen ²	Day 1 C1	Day 8 C1	Day 15 C1	Day 1 C2	D1 of C3-C16	End of Study Treatment ³⁴	Monthly Follow up ³⁵	
Baseline Demographics	X								
Medical History	X								
Physical Exam	X	X			X	At the start of each cycle	X		
Ocular Exam	X ³				X ⁴	At the start of each cycle ⁴	X ⁴	X ³⁵	
ECOG Performance Status	X				X	At the start of each cycle	X		
Vital Signs (BP, HR, Body Temperature)	X	X ⁵	X	X	X ⁵	At the start of each cycle ⁵	X		
Weight and Height	X	Weight only			Weight only	Weight only - At the start of each cycle	Weight only		
Hematology	X	X ⁶	X	X	X	At the start of each cycle	X		
Clinical chemistry	X	X ⁶	X	X	X	At the start of each cycle	X		
Urine Dipstick	X	X ⁶			X	At the start of each cycle	X		
INR, PTT	X	X ⁶	X	X	X	At the start of each cycle			
HBV/HCV tests	X								
CK-MB , Troponin	X ^{7,8}		X ^{7,8}		X ^{7,8}	At the start of each cycle ^{7,8}	X ^{7,8}		
BNP	X ⁹								
UPEP and urine Immunofixation	X				X	At the start of each cycle			
SPEP and serum immunofixation and Serum M-protein Calculation	X				X	At the start of each cycle			
Kappa, lambda free LC, FLC ratio	X				X	At the start of each cycle			

Time and Events Table for Full Study (Cycle = 21 days)									
Study Assessments ¹	Screen ²	Day 1 C1	Day 8 C1	Day 15 C1	Day 1 C2	D1 of C3-C16	End of Study Treatment ³⁴	Monthly Follow up ³⁵	
24 hr urine protein and albumin	X				X	At the start of each cycle			
IgG, IgM, IgA	X				X	At the start of each cycle			
CRP, beta2 microglobulin	X				X	At the start of each cycle			
Pregnancy Test	X ¹⁰					At the start of cycles 5 ¹⁰ , 9 ¹⁰ , 13 ¹⁰	X ¹⁰	X ¹¹	
Chest X-ray	X								
12-lead ECG	X ¹²	X ¹²	X ¹²	X ¹²	X ¹²	At the start of each cycle ¹²	X ¹²		
LVEF and valves assessment (ECHO)	X ¹³					At the start of cycles 4 ¹³ , 9 ¹³	X ¹³		
Extramedullary Plasmacytoma Imaging	X ¹⁴					At the start of cycles 5 ¹⁴ , 9 ¹⁴ , 13 ¹⁴	X ¹⁴		
BM Aspirate (see below for each test required within procedure):									
Disease assessment	X ¹⁵					At the time of Complete Response			
BCMA assessment and PD (flow)	X ¹⁶		X ^{16, 18}						
FISH testing	X ¹⁷								
BM biopsy for disease assessment	X ¹⁹					At the time of CR (disease assessment only)			
Serum (soluble BCMA)		X ²⁰			X ²⁰	Predose at the start of each cycle	X		
Serum (cytokines/chemokines)		X ²¹			X ²¹	Predose and EOI on D1 of each cycle	X		

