- If completed within 72 hrs prior to the first dose, this assessment need not be repeated on Day 1 of Cycle 1. Refer to [Table 15](#) for a comprehensive list of lab tests.
- Troponin will be measured at the local (troponin I or T) and central (troponin I) lab.
- CK-MB at the local lab or if not available by a central laboratory.
- BNP to be measured locally, or if not available by a central laboratory, at screening; if cardiac workup is required due to safety concerns during the study, BNP should be measured.

10. Perform only in women of child-bearing potential. A serum pregnancy test should be performed at screening, and subsequent pregnancy tests may be either serum or urine.
11. Final pregnancy test (serum or urine) must be performed in women of childbearing potential 60 days after last study treatment.
12. ECGs to be performed in triplicate. On dosing days, ECG to be performed at predose (within 30 minutes prior to SOI) and EOI. At screening, on interim visits (C1D8 and C1D15) and End of Study, obtain a single ECG measurement. **On days where ECG timepoints align with PK sampling timepoints, ECGs should be performed prior to PK samples being drawn (PK sample should be taken at the exact nominal time; refer to footnote 24)**
13. At Screening, LVEF may be performed within 30 days prior to first dose. All ECHOs indicated on dosing days may be performed up to 5 days before dosing. ECHOs to be done locally and sent to GSK for central imaging storage.
14. May be performed up to 21 days prior to C1D1 as screening value. Needs to be performed with the same method throughout the study as was done at baseline (i.e. if PET scan was used as baseline, subject needs to be followed by PET scans). Selected target lesion needs to be measured and followed over time.
15. Samples from within 14 days prior to first dose are acceptable.
16. Sample(s) collected for analysis at central lab. The same sample will be used for BCMA (flow) and PD. On D8 only postdose PD assessment will be performed, if applicable (refer to footnote 18).
17. FISH testing at least for: t(4;14), t(14;16), 17p13del. FISH results from samples taken within 60 days prior to first dose are acceptable.
18. **Additional samples may be collected in some subjects (up to 6) for further exploration of PD.**
19. Archival tissue from up to 60 days prior to study is acceptable.

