16. APPENDICES

16.1. Appendix 1: International Myeloma Working Group Uniform Response Criteria for Multiple Myeloma

Response	IMWG Criteria
sCR	
 CR as defined below plus normal FLC ratio and absence of clonal cells in bone marrow³ by immunohistochemistry or immunofluorescence⁴
CR	
 Negative immunofixation on the serum and urine and disappearance of any soft tissue plasmacytomas and < 5% plasma cells in bone marrow³
VGPR	
 Serum and urine M-protein detectable by immunofixation but not on electrophoresis 
or
 
 ≥ 90% reduction in serum M-protein plus urine M-protein level <100 mg/24 h
PR	
 ≥ 50% reduction of serum M-protein and reduction in 24 hours urinary M-protein by ≥90% or to < 200 mg/24 h If the serum and urine M-protein are unmeasurable,⁵ a ≥ 50% decrease in the difference between involved and uninvolved FLC levels is required in place of the M-protein criteria If serum and urine M-protein are not measurable, and serum free light assay is also not measurable, ≥ 50% reduction in plasma cells is required in place of M-protein, provided baseline bone marrow plasma cell percentage was ≥ 30% In addition to the above listed criteria, if present at baseline, a ≥ 50% reduction in the size of soft tissue plasmacytomas is also required
MR	
 ≥25% but <49% reduction of serum M protein and reduction in 24 hour urine M protein by 50-89%, which still exceeds 200 mg per 24 hour In addition to the above criteria, if present at baseline, 25-49% reduction in the size of soft tissue plasmacytomas is also required No increase in size or number of lytic bone lesions (development of compression fracture does not exclude response)
No change/Stable disease	
 Not meeting criteria for CR, VGPR, PR, or progressive disease
Progressive Disease	
 Increase of ≥ 25% from lowest response value in any one or more of the following: 
 ○ Serum M-component and/or (the absolute increase must be ≥ 0.5 g/dL)⁶ ○ Urine M-component and/or (the absolute increase must be ≥200 mg/24 h)

Response	IMWG Criteria

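### A plasmacytoma alone qualifies a Part 2 myeloma subject, but Appendix 1 cannot score its shrinkage as PR when M-protein and FLC are unmeasurable and baseline marrow plasma cells are below 30%

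*Protocol*

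**What the plan says.** **Entry.** For the Part 2 myeloma cohort, Section 5.2.1 criterion 4 sets the condition "AND has measurable disease with at least one of the following". Items a to c are serum M-protein, urine M-protein and FLC. Item d is "Biopsy proven plasmacytoma (should be measured within 28 days of Screening Visit"). No minimum lesion size or marrow percentage goes with item d.

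**Response.** Appendix 1 (Section 16.1) builds PR in steps. It rests on M-protein. If that is unmeasurable, it rests on FLC. If FLC is also unmeasurable, the rule is "≥ 50% reduction in plasma cells is required in place of M-protein, provided baseline bone marrow plasma cell percentage was ≥ 30" percent. On plasmacytomas, PR adds: "if present at baseline, a ≥ 50% reduction in the size of soft tissue plasmacytomas is also required". VGPR is defined by M-protein, and a note extends it to FLC-only disease. CR needs negative immunofixation, disappearance of plasmacytomas and few marrow plasma cells. PD may be called on definite plasmacytoma growth alone.

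**Schedule.** In Section 7.1.2.1, follow-up marrow aspirate for disease assessment is listed "At the time of Complete Response". Plasmacytoma imaging is at the start of cycles 5, 9 and 13 and at end of treatment.

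**Analysis.** Section 13.7.1 uses the All Treated population. Section 13.7.7 defines ORR as confirmed PR or better under Appendix 1 and counts unknown or missing responses as non-responses. Section 13.6.2 compares the number of responses of PR or better with Table 17.

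**The concern.** The entry rule treats the plasmacytoma as measurable disease, but below CR the response rule cannot use that measurement on its own. If M-protein and FLC are unmeasurable and baseline marrow is below 30%, a lesion that shrinks by half or more without disappearing leaves the subject at stable disease. If the same lesion grows, the subject is PD.

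This looks like an omission. Appendix 1 has a special note for FLC-only disease, which matches entry item c, and nothing equivalent for item d. The schedule requires a target lesion to be followed over time, so the measurement is collected.

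Eligibility and response definitions are fixed in the protocol, so this is not a detail left to an analysis plan. The bias runs one way: ORR is pulled down, and the cohort is more likely to meet a futility boundary or miss its final threshold when the drug works.

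**Working it through.** **1. Routes to response for a subject who qualifies only under item d**

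| Category | Requirement in Appendix 1 | Open to this subject? |
|---|---|---|
| PR by M-protein or FLC | measurable M-protein or FLC | No |
| PR by marrow | "provided baseline bone marrow plasma cell percentage was ≥ 30" percent, plus plasmacytoma shrinkage | Baseline below 30%: no. Baseline 30% or more: yes on paper, but no disease-assessment marrow is scheduled between baseline and CR |
| VGPR, first alternative | "Serum and urine M-protein detectable by immunofixation but not on electrophoresis" | Possible if M-protein is below the entry threshold but seen on electrophoresis at baseline; not if none is detectable |
| VGPR, second alternative | 90% fall in serum M-protein | No |
| CR, sCR | as above | Yes |
| PD | lesion growth is enough | Yes |

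**2. Reproducing the plan's design (Section 13.2.2)**

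Inputs from the protocol: null ORR 20%, alternative 40%, first look at 15, maximum 40, prior Beta(0.25, 0.75), stop if the predictive probability of success is below 5%.

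With x responses in n subjects and success defined as at least r responses in 40,

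PP(n, x) = P(Y ≥ r − x), where Y ~ beta-binomial(40 − n, 0.25 + x, 0.75 + n − x).

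Stop at n if PP < 0.05. Power, probability of early termination (PET) and expected sample size follow by exact binomial recursion. Of r = 11, 12 and 13, only r = 12 with a check after every subject from 15 to 39 reproduces all six stated figures:

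| | Stated | Computed |
|---|---|---|
| Type I error | 0.075 | 0.0754 |
| Power | 89.8% | 89.75% |
| PET at 20% | 88.9% | 88.85% |
| Expected N at 20% | 23.4 | 23.42 |
| PET at 40% | 8.5% | 8.49% |
| Expected N at 40% | 38.6 | 38.64 |

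The computed bounds at the planned looks (2 of 15, 4 of 22, 6 of 30) agree with Table 17. The design figures are therefore correct if every subject can be scored.

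**3. Effect of unscorable subjects**

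Let f be the share who cannot be scored as responders. The protocol does not give f, so the values below are assumptions, with no CRs in this group. The ORR that can be recorded under the alternative is 0.40 × (1 − f).

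| Unscorable | f | Recordable ORR | Power / PET, check after every subject | Power / PET, looks at 15, 22, 30 only |
|---|---|---|---|---|
| 0 of 40 | 0 | 0.40 | 89.8% / 8.5% | 90.8% / 4.6% |
| 1 of 40 | 2.5% | 0.39 | 87.5% / 10.3% | 88.7% / 5.6% |
| 2 of 40 | 5% | 0.38 | 84.9% / 12.5% | 86.2% / 6.7% |
| 4 of 40 | 10% | 0.36 | 78.6% / 17.9% | 80.1% / 9.6% |

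**4. Timing**

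Myeloma laboratory tests fall at the start of each 21-day cycle, so two assessments after baseline exist by the start of cycle 3 (2 × 3 = 6 weeks). The first scheduled plasmacytoma scan is at the start of cycle 5 (4 × 3 = 12 weeks), the next at cycle 9 (8 × 3 = 24 weeks). Two assessments make a subject evaluable for futility, so a plasmacytoma-only subject could enter the count as a non-responder before any scheduled on-treatment scan.

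**The case against.** The strongest reply is that the gap is narrow. It needs a subject who qualifies on the plasmacytoma alone, has marrow below 30% (or no follow-up marrow) and does not reach CR. Nothing in the protocol says such subjects will be common. ORR is a secondary endpoint of a Phase I study, and Section 13.6.2 leaves the stopping decision to the totality of the data, including quality of response. Section 7 also lets the timing and number of assessments change without an amendment, so an extra marrow sample is not ruled out. All of this stands and limits the size of the point. It does not supply a PR rule for a subject with marrow below 30%.

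Response is assessed by the investigator, so a site might score PR on shrinkage anyway. That would depart from Appendix 1 and could differ between sites.

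A reader might also infer two stronger points that the protocol does not support:

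- *No plasmacytoma-only subject can reach PR or VGPR.* The marrow route to PR exists at 30% or more, and the first VGPR alternative sets no baseline threshold.
- *The baseline imaging windows conflict.* Item d allows 28 days around the Screening Visit, while footnote 14 to Section 7.1.2.1 says "May be performed up to 21 days prior to C1D1 as screening value". Screening falls within 14 days before first dose, so a scan within 21 days before first dose always lies within 28 days of that visit. One scan meets both rules.

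**Conclusion.** The point holds for plasmacytoma-only subjects with no measurable M-protein or FLC and baseline marrow plasma cells below 30% (PR), and for those among them with no detectable M-protein (VGPR). At 30% or more, the PR route is written but has no scheduled test before CR. CR and sCR remain reachable and count in ORR.

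Within that group a real partial response is recorded as a non-response, so ORR is biased downward. The size depends on a share that the protocol does not state. Two such subjects in 40 would cost about five points of power (89.8% − 84.9% = 4.9), on the assumption of no CRs among them. Meeting the futility boundary is not the same as stopping, because the rule is not binding. It would be wrong to infer that the stated power is miscalculated: it reproduces when all subjects are scorable. The point should be corrected, but it does not undermine the design.

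**What to change.** Make the entry and response criteria agree, in one of two ways.

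1. **Restrict who is counted.** Require item a, b or c for subjects included in ORR and futility, so that item d alone is not sufficient. Cost: a few plasmacytoma-only subjects are left out of ORR.
2. **Add a response rule.** In Appendix 1, define response for plasmacytoma-only disease with the percentages already there: at least 50% reduction for PR and 25–49% for MR, with no new lesion and no other PD criterion. CR stays as written. State how such a response is confirmed when imaging is at cycles 5, 9, 13 and end of treatment. Count these subjects as evaluable for futility only after a post-baseline plasmacytoma scan, or after progression, death or discontinuation. Cost: a few lines of text, a few responses that rest on imaging, and possibly an added confirmatory scan, because the scheduled scans are about 12 weeks apart.

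Under either option, the stated 89.8% power again applies to a set in which every subject can be scored, provided 40 such subjects are enrolled.

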11.1.2. Male Subjects

To prevent pregnancy in a female partner or to prevent exposure of any partner to the study treatment from a male subject’s semen, male subjects must use one of the following contraceptive methods:

- Abstinence, defined as sexual inactivity consistent with the preferred and usual lifestyle of the subject. Periodic abstinence (e.g. calendar, ovulation, symptothermal, post-ovulation methods) and withdrawal are not acceptable methods of contraception.

Complete abstinence from sexual intercourse from the first dose of study medication, throughout the study treatment period and for at least 60 days after the last dose of study treatment.

- Condom (*during non-vaginal intercourse with any partner - male or female*) **OR**
- Double-barrier method: condom and occlusive cap (diaphragm or cervical/vault caps) plus spermicidal agent (foam/gel/film/cream/suppository) (*during sexual intercourse with a female*)

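### Inclusion criterion 8 accepts a prior vasectomy in place of Section 11.1.2 contraception, but Section 11.1.2 has no such exemption and also aims to keep drug in semen from partners

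*Protocol*

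**What the plan says.** Protocol Section 5.2.1, criterion 8, and the same criterion in the synopsis, cover men with a female partner of childbearing potential. Such a man "must have either had a prior vasectomy or agree to use effective contraception as described in Section 11.1.2". The criterion carries its own period, first dose to 60 days after the last dose, and one reason: "to allow for clearance of any altered sperm".

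Section 11.1.2 sets the rule for men on study. It has two aims: preventing pregnancy in a female partner and, through semen, "to prevent exposure of any partner to the study treatment from a male" subject. It then says that "male subjects must use one of the following contraceptive methods" and lists three:

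- abstinence, which is to last through treatment and "for at least 60 days after the last dose of study treatment";
- a condom, "during non-vaginal intercourse with any partner - male or female";
- a condom with occlusive cap and spermicide, "during sexual intercourse with a female".

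Vasectomy is neither a listed method nor an exemption there. Elsewhere in Section 11 it appears only in 11.1.1, as sterilisation of a female subject's partner, with azoospermia documented.

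**The concern.** The two places give a vasectomised man different instructions. Criterion 8 offers vasectomy as one arm of an either/or, with Section 11.1.2 as the other arm. Section 11.1.2 addresses male subjects without distinction.

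The difference matters because the aims differ. A vasectomy removes sperm from the ejaculate and so answers the reason given in criterion 8. It does not stop seminal fluid from reaching a partner, which is the second aim of Section 11.1.2. A site that follows criterion 8 to the letter would therefore drop the one measure that serves that aim. Section 1.2.6 expects the MMAF moiety to be genotoxic in mammalian systems, so the precaution has a stated basis. What is at stake is partner protection; no endpoint, error rate or analysis is touched.

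**Working it through.** The protocol states no statistical figure here, so the check is of the texts side by side, followed by the length of the period.

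**Who is bound.** Criterion 8: men with a female partner of childbearing potential. Section 11.1.2: male subjects, without qualification.

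**What suffices.** Criterion 8: vasectomy, or a Section 11.1.2 method. Section 11.1.2: only its three listed methods.

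**Aim.** Criterion 8: altered sperm. Section 11.1.2: pregnancy, and exposure of any partner through semen.

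**Period.** Criterion 8: first dose to 60 days after the last. Section 11.1.2: the 60 days are written under abstinence only; the condom and double-barrier items give no period.

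**Two readings of criterion 8.**

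- *Entry gate.* A vasectomised man may enrol without agreeing to Section 11.1.2 but must then follow it. The texts are compatible. The vasectomy arm then has no practical effect, since it spares him only from agreeing to something he must do anyway.
- *Literal either/or.* He need not follow Section 11.1.2 over the stated period. This is the natural reading of an alternative that carries an on-treatment window. It has an odd result: a vasectomised man whose partner is not of childbearing potential falls outside criterion 8 and stays bound by Section 11.1.2, while the man whose partner could be pregnant does not.

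The protocol does not say which reading is meant.

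**The 60-day window for barrier methods.** For a non-vasectomised man under criterion 8, that criterion supplies the window. For a vasectomised man it sits on the arm he does not take. For men outside criterion 8 (male partner, or female partner not of childbearing potential) who rely on a barrier, nothing supplies it. This second gap therefore reaches beyond vasectomised men.

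**Length of the period**, from Section 3.8 (at most 16 cycles; 21-day cycles on Schedule 1; three weekly doses in a 28-day cycle on Schedule 2), with no delays:

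- Schedule 1: dose 16 falls 15 × 21 = 315 days after the first; 315 + 60 = 375 days.
- Schedule 2: the last dose, cycle 16 day 15, falls 15 × 28 + 14 = 434 days after the first; 434 + 60 = 494 days.

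The Schedule 1 figure is not a maximum. That schedule is capped by number of cycles, and Table 13 and Section 6.3 allow doses to be withheld, in some cases beyond 14 days, which moves dose 16 later. On Schedule 2, Section 3.3.2 keeps the cycle count running when a dose is missed.

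**The case against.** The strongest reply is that there is no outright contradiction. Criterion 8 sits among the selection criteria and Section 11.1.2 among the lifestyle restrictions; a man can satisfy the first and remain bound by the second, and criterion 8 nowhere waives Section 11.1.2. This stands in part. A reader might infer that the protocol releases vasectomised men from the barrier. The documents support only that a literal reading of criterion 8 does so and that nothing in the text settles the matter.

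The preamble to Section 5.2.1 says that "adherence to the criteria as specified in the protocol is essential". That makes literal reading foreseeable, but the preamble is about who may be enrolled. Holding an eligible vasectomised man to Section 11.1.2 would not deviate from criterion 8. It is weak support and the point does not rest on it.

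A reader might also infer that partners would be exposed to a genotoxic drug. The documents do not support this. No semen concentration is given. Section 1.2.3.1 reports low free cys-mcMMAF in animals and suggests that the conjugate stays mainly in the circulation, and Section 1.2.6 says that intact conjugates do not interact directly with DNA. Nor should 375 days be read as a ceiling or as a measure of exposure.

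The stakes are small in other ways. Section 1.1 gives a median age at myeloma diagnosis of about 70, so few men are likely to have a partner of childbearing potential, and Section 13.7.8 notes that few subjects were still on treatment at the amendment. What the consent form tells these men cannot be seen. All of this limits the size of the problem; none of it removes the mismatch.

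**Conclusion.** The point holds as a minor inconsistency between two stated rules. Criterion 8 lets vasectomy stand in for Section 11.1.2 on the ground of sperm alone, while Section 11.1.2 has no such exemption and has an aim that vasectomy cannot meet. Reconciling them requires an entry-gate reading that the protocol does not state and that the criterion's own on-treatment window undercuts.

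The main issue concerns vasectomised men with a female partner of childbearing potential, an uncounted subset of the approximately 80-95 subjects of either sex. The missing barrier window concerns a wider group of men, also uncounted. The conclusion rests on one inference from outside the text, that vasectomy removes sperm but not seminal fluid. It assumes nothing about how much drug reaches semen.

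**What to change.** In the synopsis, in Section 5.2.1 criterion 8 and in Section 11.1.2, add a sentence such as: *A prior vasectomy meets the pregnancy-prevention aim only; vasectomised men must still use abstinence or a condom from first dose until 60 days after the last dose.* Leave the methods for non-vasectomised men unchanged.

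This is stricter than criterion 8 read literally. For vaginal intercourse it is lighter than Section 11.1.2 read literally, which would ask for the double barrier. The condom serves the semen aim, while cap and spermicide serve contraception, which the vasectomy already covers. If the sponsor wants the double barrier for every man, the sentence should say that instead.

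Separately, state in Section 11.1.2 that the 60-day window applies to the condom and double-barrier methods as well as to abstinence. For men outside criterion 8 this adds a post-dose period that the text does not now give them, so the amendment should present it as a change and not as a clarification.

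The cost is one sentence in three places and one clause in Section 11.1.2. The consent form should be checked for matching text.
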